**Aim 3:**

We will examine the inflammatory milieu that accompanies successful induction of the reprometabolic syndrome in Aim 1, seeking to identify candidate inflammatory modulators that may specifically contribute to the phenotype.

***Description of Population to be Enrolled:***

We will recruit up to 60 normal weight, normally cycling women aged 18-38, who will meet the criteria below:

**Inclusion Criteria:**

- BMI at least 18 but less than 25 kg/m^2

**IRB #:** 15-1052  
**Project Title:** Reprometabolic Syndrome Mediates Subfertility in Obesity  
**Principal Investigator:** [name]

- No history of chronic disease affecting hormone production, metabolism or clearance
- No use of medications known to alter or interact with reproductive hormones or insulin metabolism (e.g. thiazolidinediones, metformin)
- No use of reproductive hormones within 3 months of enrollment
- Normal prolactin and thyroid stimulating hormone levels at screening
- History of regular menstrual cycles every 25-35 days
- Use of a reliable method of contraception (female or male partner sterilization; IUD; abstinence; diaphragm)
- Normal hemoglobin A1c
- Screening hemoglobin  $\geq 11\text{gm/dl}$

Exclusion criteria:

- Women with a baseline dietary assessment indicative of  $>40\%$  daily calorie consumption from fat (as calculated based upon initial 3 day diet record) will be excluded, as the impact of increasing their dietary fat intake may be minimal.
- Women with current or a history of diabetes, prediabetes, or gestational diabetes.
- Women with fasting triglycerides  $>300\text{mg/dl}$  at screening will be excluded, as they might be at risk for acute elevation of triglycerides and even pancreatitis if placed on a high fat diet.
- Inability to comply with the protocol. Individuals who travel frequently, or who eat most of their meals outside of their home will be excluded, as it will be difficult to impossible for them to comply with the diet, to pick up the food cartons, etc.
- Because high proportions of dairy fat will be needed to attain 48% calories from fat in the diet, vegans and lactose intolerant individuals will be excluded.
- Pregnant women or women planning to become pregnant will be excluded.

***Study Design and Research Methods***

Consent/Screening Process:

A script for screening participants by telephone and by website survey who inquire in response to advertisements will be used, which will include the required verbal consent language. Participants who are eligible for enrollment will be asked to come to the Clinical and Translational Research Center (CTRC) for an intake examination and qualifying laboratory tests. Informed consent is obtained by the PI, the Professional Research Assistant, or an IRB approved designee, according to the scripted process, either when the patient comes in for the screening examination and tests or via a Zoom meeting or Telehealth with the PI or study coordinator. The informed consent discussion is always held in a private room that is free of distractions and participants are allowed the opportunity to ask questions and have their questions answered to their satisfaction before signing the informed consent document. If the participant completes the consent via Zoom meeting or Telehealth there will be a witness present and will sign the consent along with the participant. Once the Consent is signed we will request the

**IRB #:** 15-1052  
**Project Title:** Reprometabolic Syndrome Mediates Subfertility in Obesity  
**Principal Investigator:** [name]

participant to either scan the consent and email it to the Provider or take a picture with their cell phone and email it to the provider. The provider will print and sign the consent. With all signatures on the consent it will be scanned and sent to the participant. Once informed consent has been provided, baseline visit procedures are performed as outlined in the procedures section.

Study procedures:

For Aim 1a we will enroll 12 normal weight women to complete the study. For Aim 1b, we will enroll 20 normal weight women which may include women who participated in Aim 1A but not necessarily so.

Aim 1A will reproduce the reproductive phenotype of obesity in normal weight women by: infusing insulin and free FFAs in short term experiments and measuring gonadotropin pulsatility and pituitary GnRH response

Aim 1B will induce a chronic model of the reprometabolic syndrome by administering a eucaloric high fat diet for one month while monitoring gonadotropin pulsatility and daily urinary reproductive hormone excretion. In Aim 1b we want to demonstrate that a eucaloric high fat diet can induce insulin resistance and/or elements of the reprometabolic syndrome in women.

Aims 2 and 3 will be an exemption of analysis from the procedures performed and samples collected in Aims 1.A and 1.B. They will not require additional enrollment of study subjects or additional procedures.

**Pilot:** consisted of the Principle Investigator testing out the proposed diet intervention for Aim 1.B. The test diet was given for two weeks. There were no subjects consented or enrolled, and the Investigator declined compensation.

**Aim 1A:** will consist of four visits: a screening visit (12 hour fast required) and three study visits. During the screening visit participants will be provided with instructions and supplies to collect their daily morning urine and to use home ovulation predictor kits. Determining the day of ovulation will allow us to better predict the timing of the following menses (which almost always occurs 12-15 days after the urinary LH surge identified by the ovulation predictor kit). Accurate prediction of cycle Day 1 will permit more efficient scheduling of the frequent sampling studies, which must occur within a window of 1-4 days after the onset of menses (cycle days 2-5). We will ask participants to track their menstrual cycle by recording the day they start their period and the day that they ovulate and notify the study coordinator when evidence of a urinary LH surge has occurred. This will involve dipping a test stick in urine for several days to see if it changes color. Additional ovulation prediction kits will be provided if needed to the participants at the Visit 1 & 2. Participants will be administered saline only (limited subsample), saline + heparin infusion, and an insulin/intralipid/heparin infusion over 6 hours. Each participant will receive at least a saline+heparin infusion and an insulin/intralipid/heparin infusion, but

IRB #:

15-1052

Project Title:

Reprometabolic Syndrome Mediates Subfertility in Obesity

Principal Investigator: [name]

the order in which the treatments are given will be randomly assigned. The insulin/intralipid/heparin infusion will consist of 20% lipid emulsion (45ml/h), heparin (24 units/kg/hr), and insulin (20 mU/m2/min) under euglycemic clamp conditions (maintained by using dextrose). Saline will be infused at a rate of 200 ml/h with heparin (24 units/kg/hr). During the saline only visit, heparin will not be infused. We have added a 'saline only' visit to validate the findings of the saline+heparin infusion study and to rule out any independent effect of heparin. At the same time, participants will undergo a 6-hour frequent blood sampling session at each visit. Muscle oxygenation will also be measured before and at 4 hours of both infusions. Partial thromboplastin time (PTT) levels will be followed with heparin infusion adjustments as needed to avoid over-anticoagulation. Each visit will be performed in the early follicular phase of the menstrual cycle and will be completed in consecutive cycles whenever possible, but no longer than within 4 cycles from the first study. Please see table description below:

	Pre-cycle 1	Visit 1	Visit 2	Visit 3
Visit#	L0=screen	L1	L2	L3
Description/Duration	2 hours	6 hours Concurrent FSS infusion*	6 hours Concurrent FSS infusion*	6 hours Concurrent FSS infusion*
Cycle Day		2-5	2-5	2-5
History	X			
Physical	X			
Pregnancy Test		X	X	X
Routine safety labs (CBC/CMP)	X	X	X	X
Hemoglobin A1C	X			
Prolactin	X			
Fasting Lipid Panel	X	X	X	X
TSH	X			
PTT	X	X	X	X
FFA	X	X	X	X
Informed Consent	X			
Weight	X	X	X	X
Ovulation Prediction Kits	X	X	X	
Frequent blood sampling		X	X	X
Administration of GnRH		X	X	X
Muscle Oxygen Measurement		X	X	X
Infusion*		X*	X*	X*

\*participants will receive either an insulin +lipid + heparin infusion, a heparin + saline (control), or saline only in random order

IRB #: 15-1052  
Project Title: Reprometabolic Syndrome Mediates Subfertility in Obesity  
Principal Investigator: [name]

**Aim 1B:** will consist of 11 in-person visits.

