***Data Analysis Plan***

**Aim 1:**

The primary outcome will be LH pulse amplitude as assessed in the non-intervention frequent sampling study and compared to the early follicular phase study under treatment (i.e., either insulin + FFAs for Aim 1A or HFD for Aim 1B). LH pulsatility will be analyzed using a modification of the original Santen and Bardin method, as previously described and utilized by the PI in numerous studies. Up to 5 women will be assessed with frequent sampling prior to initiating the clamp portion of the study in order to confirm that diminished LH pulse amplitude is observed with the HFD. GnRH response will be compared between the non-intervention and intervention study as described above for gonadotropin pulsatility. We have used area under the curve methods to determine the LH response to exogenous GnRH and will utilize the same methodology as we have done in the past. FSH parameters will be compared between the non-intervention and intervention studies for both aims as described above for gonadotropin pulsatility. We will compare mean FSH, as pulsatility of FSH is less obvious than LH. We will compare changes in gonadotropin pulse frequency (for LH, and if we can detect distinct FSH pulses, we will compare FSH as well), mean LH and FSH and kinetics of LH, and if possible, FSH, before and after the intervention, as previously reported.

For Aim 1a, our preliminary data indicate that a sample size of 10 women should be sufficient to demonstrate short-term changes in gonadotropin amplitude, as LH pulse amplitude correlates well with mean levels in this setting. Moreover, we will be using a paired analysis. For Aim 1b, a sample size of 20 is estimated to have 80% power to detect a 25% decrement in LH pulse amplitude on the HFD using a 2 sided paired t-test, assuming  $\alpha=0.05$ , an untreated mean of 7IU/L, and a standard deviation of the difference of 1IU/ml. Urinary hormone profiles will be assessed for the entire cycle

**IRB #:** 15-1052  
**Project Title:** Reprometabolic Syndrome Mediates Subfertility in Obesity  
**Principal Investigator:** [name]

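### Aim 1A is a 12-woman crossover with no stated balance of infusion order and no period term in its paired analysis; adding both is a cheap improvement

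*Combined protocol and SAP*

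**What the plan says.** Aim 1A, under Study procedures, compares infusions within women, each given at a visit in the early follicular phase (cycle days 2-5) of a separate cycle. Visits are in consecutive cycles where possible, and no more than 4 cycles from the first.

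- Size: "For Aim 1a we will enroll 12 normal weight women to complete the study". The Data Analysis Plan for Aim 1 says that "our preliminary data indicate that a sample size of 10 women should be sufficient to demonstrate short-term changes in gonadotropin amplitude".
- Infusions: "Each participant will receive at least a saline+heparin infusion and an insulin/intralipid/heparin infusion". The saline-only visit is for a limited subsample whose size is not given.
- Order: "the order in which the treatments are given will be randomly assigned". The footnote to the visit table says "participants will receive either an insulin +lipid + heparin infusion, a heparin + saline (control), or saline only in random order". No block, sequence list or ratio is stated.
- Outcome: "The primary outcome will be LH pulse amplitude as assessed in the non-intervention frequent sampling study", compared with the study under treatment.
- Analysis: "Moreover, we will be using a paired analysis". No test is named for Aim 1A, and no period or sequence term is mentioned. The option of regression with covariates is written for the whole-cycle urinary parameters before and after the diet, which belong to Aim 1B.

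**The concern.** In a crossover, the order of visits is a known design factor. LH pulse amplitude may drift between the first and later visits for reasons unrelated to the infusion. If the analysis takes only the within-woman difference, that drift has two places to go. With unequal numbers of women in each order, part of it is added to or subtracted from the treatment contrast. With equal numbers it cancels from the contrast but widens the spread of the differences. Restricting visits to cycle days 2-5 controls cycle phase, not drift from visit to visit. The saline-only subsample adds a complication: some women have three visits and others two, so the two main infusions can fall in different pairs of visits. At stake is avoidable imprecision in the primary outcome of a very small comparison.

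**Working it through.** **Inputs.** From the protocol: 12 women, two infusions for all, a third for some, random order, paired analysis. Not in the protocol, and so assumed: the treatment effect δ and the period effect π (average shift from the earlier to the later visit), both in SDs of the within-woman difference. I take π from 0 to 1.0 SD.

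**The plan's own figure.** The 10 women come with no effect size, SD, alpha or power, so the figure cannot be reproduced. For reference, a two-sided 5% paired t-test has 80% power for 0.996 SD at 10 women and 0.889 SD at 12. I use δ = 0.889.

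**Where the shift goes.** For the two main infusions, let D be active minus control. Its expectation is δ + π if control comes first and δ − π if active comes first. With n1 and n2 women in the two orders:

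- plain paired mean: δ + π(n1 − n2)/12
- mean of the two sequence means (period-adjusted): δ

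**Chance of an unequal split under simple 1:1 randomisation (Binomial(12, 0.5)).**

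- exactly 6:6: 924/4096 = 22.6%
- 8:4 or worse: 2 × (1 + 12 + 66 + 220 + 495)/4096 = 1588/4096 = 38.8%; share of π in the estimate at 8:4 is (8 − 4)/12 = 1/3
- 9:3 or worse: 2 × (1 + 12 + 66 + 220)/4096 = 598/4096 = 14.6%; share at 9:3 is (9 − 3)/12 = 1/2

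**Averaged over simple randomisation.** n1 − n2 has mean zero, so the estimate is unbiased. Its standard error is √((1 + π²)/12): 0.29, 0.30, 0.32 and 0.41 SD at π = 0, 0.25, 0.5 and 1.0. Simulated type I error is about 5% throughout; power is 80%, 78%, 71% and 50%. Given a 9:3 split, type I error is 6.3%, 9.1% and 15.1% at π = 0.25, 0.5 and 1.0; given 8:4 it is 5.2% to 5.6%.

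**With an exact 6:6 split.** The contrast is clean, but the expected variance of D rises from 1 to 1 + (12/11)π². Simulated results at δ = 0.889:

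| Period effect π (SD) | Plain paired: type I error | Plain paired: power | With period term: power |
|---|---|---|---|
| 0 | 5.0% | 80% | 79% |
| 0.25 | 4.2% | 78% | 79% |
| 0.5 | 2.9% | 72% | 79% |
| 0.75 | 1.6% | 62% | 79% |
| 1.0 | 0.7% | 49% | 79% |

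**Price of the period term.** With two visits and 6:6, the critical t rises from 2.201 (11 df) to 2.228 (10 df), a factor of 1.012. With an unequal split the adjusted variance grows by 36/(n1 × n2): 36/32 = 1.125 at 8:4 and 36/27 = 1.333 at 9:3, and power is about 74% and 67%.

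**Three-visit case.** If 4 to 12 women have a third visit, there are 24 + 4 = 28 to 24 + 12 = 36 observations. Removing 12 woman effects, 2 infusion contrasts and 2 period contrasts leaves 28 − 16 = 12 to 36 − 16 = 20 residual df. Power for the main contrast with balanced sequences is then about 80% to 84%.

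**The case against.** Four points can be made against this.

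1. A reader might infer that the order is unbalanced. The documents do not say so: a blocked or 6:6 list would fit their wording. The 38.8% applies only if simple randomisation is used. This stands, although a balanced list alone does not recover the power shown in the 6:6 table.
2. A reader might infer that the test is invalid or carries an inflated false-positive rate. Averaged over simple randomisation it does not, and with 6:6 it is conservative. The bias, and the inflation at 9:3, are conditional on the split that occurs. This stands.
3. A crossover model with a period term is also a paired analysis, and no test is named. That is true, but nothing in the text for Aim 1A points to a period term, and the preliminary crossover described under Figure 4 used paired t tests.
4. The size rests on assumptions. At a treatment effect of 1.25 SD, a 0.5 SD period effect costs only 2 to 4 points. The Aim 1B inputs give 7 × 0.25/1 = 1.75 SD, at which 12 women keep at least 99.5% power even with a 0.75 SD period effect. The dependence on assumptions stands, but the Aim 1B inputs are a weak guide: they need only 5 women for 80% power, not the 20 stated. Nor does a period term remove random cycle-to-cycle variation; it removes only a shift common to the women.

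A further objection, that three visits use up too many degrees of freedom, fails: the added observations more than pay for the added terms.

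**Conclusion.** The point holds as a cheap improvement to a valid randomised comparison, not as a flaw that invalidates it. The plan specifies neither balance nor a period term, and at 12 women either omission leaves avoidable error in the primary outcome if visits shift systematically. For a treatment effect of 0.889 SD and a 6:6 split, the loss against the period-adjusted analysis is about 1 point of power at a period effect of 0.25 SD, 7 at 0.5, 17 at 0.75 and 30 at 1.0. Whether any such shift exists cannot be settled from the documents, and a larger treatment effect makes the loss smaller.

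**What to change.** Specify a linear mixed model for LH pulse amplitude on all Aim 1A visits, with infusion and period as fixed effects and woman as a random effect. Take the insulin + lipid + heparin versus saline + heparin contrast from it. Fix the model before the outcome data are examined, and do not make the period term depend on a test for period. Visit order is recorded by design, so this can be done even if enrolment is complete.

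For women not yet randomised, use a balanced sequence list (for example 6:6 for the two main infusions) that also states how many women have the saline-only visit and where it falls.

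The cost is a list and one model statement. With balanced order and no period effect, about 1 point of power is lost in the two-visit case and none in the three-visit case. If the realised order is already unequal the price is higher: power of about 74% at 8:4 and 67% at 9:3, against 80% unadjusted, when there is no period effect. That is a further reason to balance the order while it is still possible. No dose, visit or sample changes.

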### Screening

**Verbal screening:** At the time of verbal screening for this aim, participants will be provided with a 3 day food diary by email. They will be asked to complete the diary and bring it with them to the screening visit. Participants will also be instructed to fast for 12 hours prior to their in-person screening visit.

**Zoom meeting or Telehealth:** This is an optional visit to complete the study consent and the history prior to the in-person screening in order to reduce the number of persons to which the participant will be exposed. Please see the previous section “Consent/Screening Process” for details on how a signed copy will be obtained. **In-person screening:** If the history and consent were not obtained via a Zoom meeting or Telehealth appointment , they will be completed at this in-person visit. Participants will have a physical completed. We will perform a urine pregnancy test, obtain their current medications, their height and weight, a blood sample for screening labs (CBC/CMP, lipid panel), and review their 3-day food diary and food preferences. They will also undergo a DEXA procedure. After examining the results of these tests, we will confirm if the participant meets the inclusion/exclusion criteria. Participants will be provided with instructions and supplies to collect their daily morning urine and to use home ovulation predictor kits. Determining the day of ovulation will allow us to better predict the timing of the following menses (which almost always occurs 12-15 days after the urinary LH surge identified by the ovulation predictor kit). Accurate prediction of cycle Day 1 will permit more efficient scheduling of the frequent sampling studies, which must occur within a window of 1-4 days after the onset of menses (cycle days 2-5). We will ask participants to track their menstrual cycle by recording the day they start their period and the day that they ovulate and notify the study coordinator when evidence of a urinary LH surge has occurred. This will involve dipping a test stick in urine for several days to see if it changes color. At the conclusion of the screening visit or prior to Visit 1.1 we will provide each participant (from August 2019 and on) with a fecal collection kit to bring back to Visit 1.1 to obtain a pre-diet collection.

[figure not shown]
### Cycle 1

**Visit 1.1:** Prior to initiating further study procedures, participants will be provided with a Fitbit. They will be asked to use the Fitbit and collect daily morning urine starting on day 1 of their next cycle (Cycle 1) until Visit 8 (the start of Cycle 5). At the beginning of their first cycle (between days 2-4), participants will

IRB #: 15-1052  
 Project Title: Reprometabolic Syndrome Mediates Subfertility in Obesity  
 Principal Investigator: [name]

have a pregnancy test, have their height and weight recorded, and provide a blood sample for safety labs (CBC/CMP) as well as hormones (AMH), cytokines. Ketones will be measured by study personnel or nurse using a urinary test strip on discarded urine used for the pregnancy test. We are proposing to look at urinary ketones because we want to ensure we are not inducing a ketogenic state in the participants. Participants will undergo a 6-hour frequent blood sampling study (FSS) to examine LH pulsatility and GnRH responsiveness. Gonadotropin pulsatility is assessed by withdrawing 3cc of blood every 10 minutes from an indwelling IV catheter. At 4 hours a physiologic bolus of GnRH 75 ng/kg will be administered to assess pituitary LH response and q10minute sampling will continue for the remaining 2 hours. This is described in the figure below. To avoid wasting any blood, a closed tubing system is used when a nurse is available. Blood is withdrawn into the tubing and the sample is taken without discard from a proximal IV port. When a nurse is not available, a lab technician will use gravity tubing to draw the blood. At the end of the visit a small amount of blood will be drawn for another CBC/CMP. Participants will be provided breakfast and lunch during this visit.

#### Data Summary for our 6 in-patient visits (4 clamps, 2 FSS-only)

**Visit 1.2:** After the 1.1 visit, the participants will return after fasting overnight. They will have their height and weight recorded. They will provide a blood sample for baseline safety labs (CBC/CMP, lipid panel, FFAs). Additional blood samples are drawn during the basal period, and Stages 1 and 2 of the HEC to assess insulin, FFAs and glycerol. Participants will have 2 IV lines placed in their arm for infusion of insulin (constant) and 20% dextrose (variable, as needed to maintain euglycemia, defined as a blood glucose of 90-110 mg/dl) and glucose monitoring. A HEC will be performed for 3 hours (180 minutes). Plasma glucose is measured every 5 minutes, with concentrations determined immediately upon collection, and the glucose infusion rate adjusted to maintain euglycemia throughout the HEC. At the end of the visit they will provide another blood sample for safety labs and will be provided with lunch.

IRB #: 15-1052

Project Title: Reprometabolic Syndrome Mediates Subfertility in Obesity

Principal Investigator: [name]

Participants will be provided a three month supply of iron supplements and be instructed to take one 325mg tablet daily for the next three months.

## Cycle 2

With the onset of the next menstrual period (Menses #2, start of Cycle #2), a eucaloric, high fat diet (48% energy from fat) will be administered. Participants will continue collection of daily morning first urine, use their Fitbit, and intake of iron supplements over the course of Cycle 2. Also, participants will be asked to use home ovulation predictor kits.

**Visits 2-5:** Participants will be asked to pick up meals twice per week, return their empty food containers, and will be asked if they have any questions about the diet. At the first meal pick-up each week, they will also have their weight recorded, and they will provide a fasted blood sample for fatty acid analysis. At each of these visits, they will return their collected urine and receive more urine collection supplies. The study team will either review the fitbit information and go over questions about the diet in person or via a phone, zoom, or skype call. In addition to the aforementioned supplies we will also provide each participant with a second fecal collection kit to obtain a post-diet fecal sample.

## Cycle 3

Participants will continue collection of daily morning first urine, use their Fitbit, and intake of iron supplements over the course of Cycle 3.

**Visit 6.1:** At the beginning of their third cycle (between days 1-4), participants will report to the inpatient CTRC. This visit will be identical to visit 1.1 except participants will eat their high fat diet.

**Visit 6.2:** After visit 6.1, and after fasting overnight, the participants will return for a repeat of Visit 1.2.

After Visit 6.2, participants will resume their normal diet.

## Cycle 4

Participants will continue collection of daily morning first urine, use their Fitbit, and intake of iron supplements over the course of Cycle 4.

[figure not shown]
**Visit 7:** At the start of their fourth cycle, participants will have urine pregnancy test and their weight recorded, will return their collected urine, empty iron supplement bottle(s), undergo a DEXA procedure. The study team will review their Fitbit information with the participant either in person at visit 7 or via phone, zoom, or skype call.

IRB #: 15-1052  
 Project Title: Reprometabolic Syndrome Mediates Subfertility in Obesity  
 Principal Investigator: [name]

## Cycle 5

**Visit 8:** At the beginning (between days 2-5) of the participant's fifth cycle they will be asked to fast overnight and come in for a visit. They will have a history and physical completed, and we will obtain their current medications, their height and weight, and a blood sample for labs (CBC/CMP, lipid panel). Participants will return their collected urine samples. The study team will review their Fitbit activity and answer any questions either in person at visit 8 or via a phone, zoom, or skype call. A follow-up email will be sent out with a REDCap link to an anonymous exit survey to better predict pitfalls of the study. In the event that a participant does not see the study to completion, the anonymous survey will be sent to them upon confirmation of withdrawal/elimination.

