**Aim 2 Secondary outcomes:**

1. *Insulin, glucose and FFAs* will be measured by the CTRC laboratories. Plasma non-esterified FFAs will be measured after lipid extraction of plasma (Wako Diagnostics, Richmond, VA). Lipids are measured by enzymatic methods (Quest Diagnostics- Nichols Institute, Chantilly, VA). Ketones will be measured by the study personnel using a urinary strip on discarded urine used for pregnancy test.
2. RBC lipids will also be compared, as we predict that the HFD will result in increased omega-6 rich FFAs and less omega-3 FFAs.
3. *DEXA body composition* will be measured before and after the intervention. [name] will collaborate with the PI, as she has in the past, on these measurements.
4. Weight will be monitored weekly to assure that participants are not losing or gaining weight, which could affect study results. A weight gain or loss of more than 1.5lbs in one week will alert the study staff to counsel the participant and/or adjust the HFD food modules.

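### The only post-diet DEXA in the visible visit text comes about 3 to 5 weeks after the diet ends, so it measures the diet plus a recovery cycle, not the end-of-diet effect

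*Combined protocol and SAP*

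**What the plan says.** All references are to the combined protocol and SAP.

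- **Outcome.** Aim 2 Secondary outcomes, item 3: DEXA body composition "will be measured before and after the intervention".
- **First scan.** Aim 1B, In-person screening: "They will also undergo a DEXA procedure". Women are told to fast for 12 hours before this visit.
- **Diet.** It starts with the menses that open Cycle 2. It ends early in Cycle 3: "After Visit 6.2, participants will resume their normal diet".
- **End-of-diet visits.** These are defined as copies of baseline visits. For Visit 6.1: "This visit will be identical to visit 1.1 except participants will eat their high fat diet". For Visit 6.2, after an overnight fast: "the participants will return for a repeat of Visit 1.2". The descriptions of Visits 1.1 and 1.2 mention no DEXA.
- **Second scan.** Visit 7, start of Cycle 4: "participants will have urine pregnancy test and their weight recorded", and in the same list women "empty iron supplement bottle(s), undergo a DEXA procedure".
- **Primary outcomes.** LH pulse amplitude comes from the sampling study at Visit 6.1, and M from the clamp at Visit 6.2. Both are measured before the diet stops.

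**The concern.** Aim 2 asks what metabolic changes the induced syndrome brings about. Its primary outcome is read while the woman is still on the diet. Body composition, in the same aim, is read about a cycle later, after she has gone back to her usual food. The two results describe different states.

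A diet-related shift between fat and lean mass that reverses off diet could be missed, and a shift that arises off diet could be credited to the diet. Weight is recorded at Visit 6.2 (as a repeat of Visit 1.2) and at Visit 7, so a net weight change over the gap would show. A change in composition at constant weight would not.

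No reason for the later scan is given. The recovery follow-up under Risks of a high fat diet names reproductive hormones, lipid panels and safety labs, but not body composition.

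**Working it through.** The plan gives no figure for the scan timing, so there is none to reproduce. The interval follows from the visit windows.

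**Inputs**
- L, cycle length: 25-35 days (Inclusion Criteria).
- Diet start: Cycle 2 day 1 (Aim 1B, Cycle 2).
- Visit 6.1: Cycle 3 days 1-4 (Aim 1B, Cycle 3).
- d, the Cycle 3 day of Visit 6.2: the text says only that it follows Visit 6.1 and an overnight fast. Assumed to be the next day, so d = 2-5.
- v, the Cycle 4 day of Visit 7: not stated. Assumed to be 1, with 5 as the upper limit.

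**Elapsed days from diet start to Visit 6.2** = L + d - 1
- Shortest: 25 + 2 - 1 = 26
- Longest: 35 + 5 - 1 = 39

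**Days off diet at the Visit 7 scan** = L + v - d
- v = 1: 25 + 1 - 5 = 21 to 35 + 1 - 2 = 34 days (3.0 to 4.9 weeks)
- v = 5: 25 + 5 - 5 = 25 to 35 + 5 - 2 = 38 days (up to 5.4 weeks)
- If Visit 6.2 may be up to 3 days after Visit 6.1, d can reach 7 and the minimum becomes 25 + 1 - 7 = 19 days.

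The first formula uses the length of Cycle 2 and the second that of Cycle 3, so unequal cycles within 25-35 days leave both ranges unchanged.

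**A typical case.** Take a 28-day cycle with Visit 6.1 at mid-window (day 2.5), so d = 3.5 and v = 1. On diet: 28 + 3.5 - 1 = 30.5 days. Off diet: 28 + 1 - 3.5 = 25.5 days. The time off diet is nearly as long as the exposure.

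**If the scan is moved**
- To Visit 6.2: 26-39 elapsed days after diet start, before normal eating resumes.
- To Visit 6.1: 25 + 1 - 1 = 25 to 35 + 4 - 1 = 38 elapsed days after diet start.
- Time off diet is 0 days in either case.
- Cycle 1 day 1 to the second scan: now 3 × 25 = 75 to 3 × 35 = 105 days. At Visit 6.2 it would be 2 × 25 + 2 - 1 = 51 to 2 × 35 + 5 - 1 = 74 days. At Visit 6.1 it would be 50 to 73.

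**What each scan estimates.** Let D be the change from screening to the end of the diet, and R the change between then and Visit 7. A scan at Visit 6.2 estimates D; one at Visit 7 estimates D + R. The documents give no value for R, so the size of any error in body composition cannot be stated.

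**The case against.** **The absence of an end-of-diet scan is not fully established.** The Aim 1b timetable is not shown in our copy, and the visit narrative is not exhaustive. Normal prolactin, TSH and hemoglobin A1c are required for entry but are not among the Aim 1B screening labs. Inhibins are to be measured before and after the intervention, but Visit 1.1 names only AMH. A post-diet fecal kit is issued with no return visit listed. This stands as a reason to check the timetable first. It does not undo the explicit placement of a scan at Visit 7.

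**Visit 7 is literally after the intervention.** It also falls at about the end of the window of two cycles from diet start used for urinary hormones. A reader might infer that the visit text contradicts the outcome definition. It does not: the words are satisfied, and the fault is one of fit to the aim. The two-cycle window is set for urinary hormones, however, and gives no reason for the DEXA timing.

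**The plan holds weight steady.** The diet is eucaloric, and a change above 1.5 lb in a week prompts counselling or adjustment of the food. This limits any composition effect on diet, though it does not exclude one.

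**The gap is not unobserved.** A reader might infer that activity goes unmeasured after the diet. No visit is listed between 6.2 and 7, and weekly activity monitoring is specified only for the diet month. But the Fitbit is worn through Cycles 3 and 4 and reviewed at Visit 7, and monthly monitoring runs throughout.

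**Conclusion.** The point holds as a mismatch between the timing of one secondary outcome and the aim it serves. On the visible text, the DEXA change estimates the diet plus about one recovery cycle: 21-34 days off diet, up to 38 with a late Visit 7, and 19 at the least if Visit 6.2 is delayed. This rests on 25-35 day cycles, the assumed days for Visits 6.2 and 7, and there being no further scan in the timetable that is not shown.

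The consequence is probably small. A reader might infer that Aim 2 as a whole is compromised, or that a real effect on body composition will be lost. The documents support neither: M and LH pulse amplitude are measured on diet and are unaffected, and nothing in the plan shows how large a composition change to expect or how fast it would reverse. This is an inexpensive improvement, not a defect that must be repaired before the study can be interpreted.

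**What to change.** First confirm that the Aim 1b timetable lists no end-of-diet scan. If it lists none, move the existing second DEXA from Visit 7 to one of the end-of-diet visits:

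- **Preferred: Visit 6.2, on arrival.** The woman is fasted, as at the screening scan, and has not yet returned to her usual diet. Visit 1.2, which this visit repeats, lists no pregnancy test, so use the one from Visit 6.1 or do one that day.
- **Otherwise: Visit 6.1, before the IV is placed.** As a copy of Visit 1.1, where women "have a pregnancy test, have their height and weight recorded", it already includes a pregnancy test. No fast is stated for this visit, and breakfast is provided, so the match to screening is weaker.

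The change is one line in the visit schedule, with no extra scan, radiation or visit. A woman who leaves the study after the end-of-diet visits would still contribute a DEXA pair. The costs are booking DEXA on a study day and losing the post-withdrawal reading. Cycle 1 would still lie between the two scans and add some noise.

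If Visit 7 is kept, change only the label: report the result as change from screening to about one cycle after the diet, not as the end-of-diet effect.
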